11. SAFETY ANALYSES

11.1 Ocular Adverse Events

The primary safety analyses will be based on the as-treated population, defined as subjects who are randomized and receive at least one dose of study agent. Safety endpoints will include ocular adverse events, ophthalmic exam findings, and use of rescue treatments. The occurrence of ocular adverse events will be recorded from the time of randomization through the last study visit. AEs will be categorized by System Organ Class and Preferred Term using the Medical Dictionary for Regulatory Activities (MedDRA) and by severity using the Common Terminology Criteria for Adverse Events dictionary.

In general, all AE tables will be presented by treatment group, causality and severity. The following will be summarized and presented overall and by treatment group:

- The number and percentage of subjects experiencing an SAE
- The number and percentage of subjects experiencing an SAE by preferred term and by severity of event
- The number and percentage of subjects experiencing an SAE by preferred term and by relationship to study drug
- The number and percentage of subjects experiencing an AE
- The number and percentage of subjects experiencing an AE by preferred term and by severity of event
- The number and percentage of subjects experiencing an AE by preferred term and by relationship to study drug
- The number and percentage of AEs that cause a subject to discontinue study drug
- The number and percentage of AEs leading to death.

Adverse events will be coded using the Medical Dictionary for Regulatory Activities (MedDRA) central coding dictionary. Adverse events will be described in summary tables and in individual listings for the DSMB reports.

Primary reporting of Adverse Events will include the Safety Population, and reported overall as well as by the actual treatment that each subject received. Rates of adverse events will be compared between the two treatment groups using chi-squared type approaches. In most instances, exact approaches will be implemented that maximize the statistical power to detect a treatment difference. Specifically, when exact approaches are appropriate, the mid-*p*-value correction¹⁴ will be implemented, whereby the probability value of obtaining a result at least as extreme as observed is reduced by one half of the probability of obtaining the specific result observed. This is directly calculable in SAS, for example, as the Fisher's exact test output gives these two probabilities directly.

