5.4 Assessment of Primary Endpoint(Safety)

Safety and tolerability will be evaluated by the PI from the findings of scheduled eye examinations at days 1 (day of surgery) through 8 (in-person follow-up visit) and at months 1, 3, 6 and 12 after initiation of pAF therapy. More frequent safety evaluations may be performed if clinically indicated or at the discretion of the investigator. Information from the eye examination at these additional safety evaluations will be collected and entered into the EDC as adverse events as appropriate.

All ocular adverse events will be recorded from randomization through Month 12. Any events that occur from time of consent to randomization will be recorded as medical history.

6 Safety Monitoring

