6.1 Adverse Event Reporting

The site investigator is responsible for evaluating all adverse events at their Clinical Center and ensuring that they are properly reported. Only ocular adverse events (as specified in 6.1.2) that occur during this study will be recorded. The nature of each experience, date and time

(where appropriate) of onset, outcome, course, and relationship to treatment will be documented.

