6.1.2 Classification of an Adverse Event (Relatedness, Severity, and Expectedness)

Relatedness: The suspected relationship between study interventions and any adverse event will be determined by the site investigator using the criteria below. Relatedness must be assessed by an investigator and may not be assessed by a research coordinator.

- Not Related: The event is clearly related to other factors, such as the subject's clinical state, therapeutic interventions, or concomitant drugs administered to the subject.
- Possibly Related: The event follows compatible temporal sequence from the time of beginning the assigned study intervention, but could have been produced by other factors such as the subject's clinical state, therapeutic interventions, or concomitant drugs administered to the subject.

- Probably Related: The event follows a reasonable temporal sequence from the time of beginning the assigned study intervention, and cannot be reasonably explained by other factors such as the subject's clinical state, therapeutic interventions, or concomitant drugs administered to the subject.

Severity:

The severity, which is a measure of intensity, of clinical adverse events and laboratory abnormalities will be recorded by the site investigator and categorized. The following guidelines will be used to describe severity.

- Mild: The event requires minimal or no treatment and does not interfere with the participants daily activities.
- Moderate: The event results in a low level of inconvenience or concern with the therapeutic measures. Moderate events may cause some interference with functioning.
- Severe: The event interrupts a participants usual daily activity and may require systemic drug therapy or other treatment. Severe events are usually potentially life-threatening or incapacitating. Of note, the term "severe" does not necessarily equate to "serious".

Expectedness of the Event:

All adverse events, including serious adverse events, will be evaluated as to whether their occurrence was expected or unexpected. An AE will be considered unexpected if the nature, severity, or frequency of the event is not consistent with the risk information described for the study intervention. The following events will be reported as AEs::

- Infection
- Delayed healing of the epithelial defect (after the 7-day post-surgery visit)
- Scarring or haze
- Severe irritation of conjunctiva or periocular skin in the first week

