- Poor refractive outcome (worse than 20/40 at 3 months or beyond)
- Pain or severe irritation at 3 months or beyond
- Corneal erosion
- Corneal haze
- Need for touch up surgery

There is a theoretical risk of infection with amniotic fluid drops. A patient could have an immune reaction to the study drops.

6.1.3 Treatment or Action Taken:

For each adverse event, the site investigator will record whether an intervention was required:

- Medical or surgical procedure
- Concomitant medication: started, changed, or discontinued
- Other, specify
- No action taken

6.1.4 Outcome of Event:

Finally, the site investigator will record the clinical outcome of each adverse event as follows:

- Death
- Recovered and the patient returned to baseline status
- Recovered with permanent sequelae
- Symptoms persist

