4. STUDY METHODS

4.1 Overall Study Design and Plan

The pAF after PRK trial will randomize approximately 60 eligible and consented patients to post-PRK treatment for 7 days starting on the day of surgery, with pAF or placebo delivered in a double-blind fashion, in a 1:1 ratio. Treatment with the assigned therapy is to commence immediately after surgery, with the patient receiving the first dose prior to leaving the surgery center.

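### Ocular AEs are tabulated and compared over one window, randomization to Month 12, although the drops are given for 7 days; late PRK events can dilute an early excess, and tables by onset period should be added

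*SAP*

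**What the plan says.** SAP 4.1 describes "post-PRK treatment for 7 days starting on the day of surgery". Protocol 5.4 sets the safety window: "All ocular adverse events will be recorded from randomization through Month 12". SAP 11.1 repeats it: "The occurrence of ocular adverse events will be recorded from the time of randomization through the last study visit".

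SAP 11.1 then lists tables of subjects with any AE and any SAE, and the same by preferred term with severity and by preferred term with relationship to study drug. On testing it says: "Rates of adverse events will be compared between the two treatment groups using chi-squared type approaches". It adds: "In most instances, exact approaches will be implemented that maximize the statistical power to detect a treatment difference". The exact method named is Fisher's test with the mid-p correction. Protocol 12.6 has the same tables. Neither section splits any AE table or test by time of onset.

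The list of reportable events in Protocol 6.1.2 mixes early and late outcomes. At one end is "Severe irritation of conjunctiva or periocular skin in the first week". At the other is "Poor refractive outcome (worse than 20/40 at 3 months or beyond", together with pain or severe irritation from 3 months on and touch-up surgery. Infection, corneal erosion and haze carry no timing. Protocol 6.1 requires the date of onset to be documented for each event.

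**The concern.** In the any-AE table, a patient whose only event is a surgical outcome at Month 3 or later counts the same as a patient who reacted to the drops in week 1. If late surgical outcomes are equally common in the two arms, adding them raises both proportions, narrows the gap between them and adds variance. An early excess on pAF then becomes harder to see, and the comparison moves towards no difference. For a trial whose primary objective is safety, that is the less cautious direction in which to err.

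The planned breakdowns help, but they do not give a randomized comparison by period. Preferred-term coding carries no onset split. Severe irritation is on the list both for the first week and from 3 months on, and the documents do not say whether the two would be coded apart. An early excess spread over several terms would show in no single one. Relatedness is judged by a masked investigator, and Protocol 6.1.2 lets an event be called possibly related on compatible timing even when other causes could explain it.

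**Working it through.** **The plan's own figure.** The only power figures in the documents are the detectable differences in healing time (SAP 6; Protocol 12.5). They reproduce to within 0.01 day. For example, 0.5 × √((1+0.5)/2) × √(2/28) × (1.960+0.842) = 0.324, against the stated 0.33 days. No hypothesis, margin, alpha or power is given for safety, so there is no safety figure to reproduce.

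**Inputs.**
- Patients per arm: 30 (60 enrolled in SAP 6, allocated 1:1 in SAP 4.3).
- Test: two-sided Fisher mid-p (SAP 11.1).
- Level: 0.05, assumed.
- Early risk (onset by Day 8): 5% on placebo and 25% on pAF, assumed.
- Late background risk L: equal in both arms and independent of early events, assumed and varied.

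The documents give no AE rates.

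**Formulas.**
- The 12-month risk of any AE in an arm with early risk e is 1 − (1−e)(1−L). The difference between arms shrinks from 20 points to 20 × (1−L) points.
- Power is the sum, over all pairs of counts (x, y), of Bin(x; 30, p0) × Bin(y; 30, p1), taken where the Fisher two-sided p minus half the probability of the observed table is at most 0.05.

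**Results, 5% v 25%.**

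| Late rate L | 12-month risk, placebo v pAF | Power | Share of undiluted power lost |
|---|---|---|---|
| 0 (early window) | 5.0% v 25.0% | 53% | – |
| 2% | 6.9% v 26.5% | 47% | 12% |
| 5% | 9.75% v 28.75% | 39% | 25% |
| 10% | 14.5% v 32.5% | 31% | 41% |
| 15% | 19.25% v 36.25% | 26% | 51% |
| 20% | 24.0% v 40.0% | 22% | 59% |
| 30% | 33.5% v 47.5% | 15% | 72% |

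Shares are taken from unrounded powers. As a worked row, at L = 10% placebo is 1 − 0.95 × 0.90 = 0.145 and pAF is 1 − 0.75 × 0.90 = 0.325.

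**Other early risks** (power at L = 0, 5%, 10%, 20%, 30%).
- 5% v 20%: 34%, 24%, 19%, 14%, 10%.
- 5% v 30%: 70%, 56%, 45%, 32%, 22%.
- 5% v 40%: 92%, 82%, 73%, 55%, 40%.

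The late rate at which half the power is gone is nearer 15% for the smallest excess and nearer 25% for the largest.

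**Enrolment.** Protocol 12.5 enrols 63, not 60. With 32 and 31 patients, power for 5% v 25% is 58% to 66% undiluted and 25% to 29% at L = 20%, depending on which arm has the extra patient. The pattern is the same.

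**The case against.** **A reader might infer that the safety comparison loses most of its sensitivity.** The documents do not support that. They give no late AE rates, and Protocol 3.1 describes delayed healing, recurrent erosion and dry eye after PRK as rare. At late rates of 2% to 10% the 5% v 25% case keeps roughly three fifths to nine tenths of its power. A loss of more than half needs late rates that are only assumed.

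**A reader might also infer that an early table should become the lead safety comparison.** That does not follow. Delayed healing is defined in Protocol 6.1.2 as occurring after the 7-day visit, and haze or a poor refractive outcome would also arise later. By the same calculation, take a late excess of 5% v 25% with an early background of 0 to 20% in both arms. The Day 8 table would flag it about 0 to 3% of the time, and the pooled table 53% down to 22%. Each window is blind to something.

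**The any-AE rate is not the only analysis.** Nothing in the SAP names it as the lead. If an early excess sat in one preferred term with no late events, that term's comparison would have the same 53% power. A late complication judged not related to the drops can be set aside in the relatedness tables. Both points stand in part: they work for a concentrated excess and for clear-cut relatedness, not for an excess spread over terms or for doubtful relatedness.

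**Early safety is already looked at.** The DSMB meets when data for at least the first 8 days are available on about 5, 30 and 60 patients (SAP 5.1.1), and first-week pain and pain medication are compared separately. This lowers the risk that an early problem passes unseen during the trial. It does not put an early AE comparison in the final report.

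**Sample size is the main limit.** This stands. Without any dilution, 5% v 20% has only 34% power, and no events in 30 patients leaves a one-sided 95% upper bound of 1 − 0.05^(1/30) = 9.5%.

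The sentence in SAP 11.1 that gives the window is about recording. The sentence on the comparison states no period at all, so the full window is simply what applies by default.

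**Conclusion.** The gap is real and moderate. Seven days of dosing are assessed through AE tables and tests that cover 12 months and are not split by onset, and the planned breakdowns separate early from late events only in part.

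For assumed early risks of 5% v 25% at 30 per arm, pooling costs about a quarter of the power at a late rate of 5%, two fifths at 10% and more than half from roughly 15%. These sizes rest on three assumptions: the early risks, a late rate equal in both arms, and independence of early and late events. None can be checked from the documents.

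This is a cheap improvement in specification. It does not show that the safety objective fails or that the 12-month window is wrong.

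**What to change.** In SAP 11.1 and Protocol 12.6, prespecify that the listed subject-level AE tables and the mid-p comparison are also produced by onset period:

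1. onset from first dose through the Day 8 visit;
2. onset after the Day 8 visit through Month 12.

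Report the two side by side with the pooled 12-month table, which is kept and not demoted, and name no period as the lead. State that an event belongs to the period of its onset, that a patient with events in both periods counts in both, and how an event first seen at the Day 8 visit is assigned.

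The cost is a few sentences and further runs of tables already planned, using onset dates already collected. The downside is more unadjusted safety comparisons. SAP 8.4 already commits to noting in every report that multiple safety outcomes were evaluated. Fixing the cut-point before unblinding avoids a post hoc choice.

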Pre-operatively each patient will be randomized to one of two post-operative drop regimens. Neither the patient nor their doctors will know if they are receiving pAF or placebo. The vials containing pAF and placebo (NaCl 0.9%, Baxter Medical) will be packaged the same by the Cell Therapy and Regenerative Medicine (CTRM). The assigned drop will be administered in both eyes throughout the study.

Regimen 1 will serve as the placebo control. For the first week only, patients in this regimen will receive placebo saline solution (NaCl 0.9%, Baxter Medical) for use four times daily. Patients will otherwise be treated with our standard post-operative drop regimen, which includes prednisolone acetate 1% suspension (4x/day for 7 days, then 2x/day for 2 additional weeks), moxifloxacin 0.3% (4x/day for 7 days), and ketorolac 0.5% (2x/day for 3 days only). The prednisolone acetate will be tapered to fluorometholone 0.1% suspension (3x/daily on days 22-60 then 2x/daily on days 61-90). A bandage contact lens will also be placed following surgery as is standard care for PRK patients.

Regimen 2 will have a bandage contact lens placed post-PRK and have an identical drop regimen with the exception of replacing the placebo saline with pAF four times daily for one week.

All patients will be instructed to use supplemental preservative free artificial tears from individual vials (any brand) no less than 3 but up to 8 times a day in both eyes the first week. After the first week, they will continue to be allowed use of preservative free tears as needed per the standard post PRK regimen in our center.

Patients are instructed to use oral medications as needed post-surgery. Ibuprofen or naproxen may be helpful in preventing pain for the first 3 days following the procedure. Patients will also be prescribed hydrocodone-acetaminophen 5-325 mg every four hours as needed for breakthrough pain. Patients will record how many pain pills are taken each day on a worksheet provided by the research team after the surgery.

The patients will have a pain rating sheet and will be asked to grade their peak subjective pain on a scale of 0 to 10 (with 10 being the most painful) for the first 7 days. They will grade each eye separately.

The day of surgery will be designated day 1, as surgery occurs in the early morning. The size of the epithelial defect created by PRK will be measured at the time of surgery completion.

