Surgeons will administer the first dose of masked study drug (placebo or pAF fluid) directly after surgery, the morning of day 1, and three more times that day. Patients will then administer drops four times a day total for the next 6 days, for a total of 7 days of study drug administration. The patients will begin filling out the pain survey the night of day 1.

At a designated time on day 1 (2nd visit post-surgery), 3, 4, 5, 6, 7, and 8 each patient will be examined by one of the study investigators who will be masked to the drop regimen. The investigator will grade the size of the epithelial defect on day 1(AM), 3, 4, 5, 6, 7, and 8 by measuring the largest horizontal and vertical meridians using slit lamp biomicroscopy. If a patient has re-epithelialized by an earlier exam day (i.e., day 3) they will be able to skip all subsequent in person examinations except for day 8 (i.e., skip days 4, 5, 6, and 7). All patients will still need to record their pain rating scale at the end of each day and return for the day 8 visit.

The study investigators will be masked to which drop is being used for each patient. Patients will be required to store all drops in the freezer and will be masked as to which type of drop is being used.

Patients will also be seen at post-operative months 1, 3, 6 and 12. At each of these visits visual acuity and manifest refraction will be checked, along with a measure of ocular surface staining and corneal regularity. These are all standard procedures performed for post-operative PRK patients regardless of study participation.

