12.6 Analysis of Safety Data

The primary safety analyses will be based on the as-treated population, defined as subjects who are randomized and receive at least one dose of study agent. Safety endpoints will include ocular adverse events, ophthalmic exam findings, and use of rescue treatments. The occurrence of ocular adverse events will be recorded from the time of randomization through the last study visit. AEs will be categorized by System Organ Class (SOC) Preferred Term (PT) using the Medical Dictionary for Regulatory Activities (MedDRA) and by severity using the Common Terminology Criteria for Adverse Events (CTCAE) dictionary.

In general, all AE tables will be presented by treatment group, causality and severity. Events in the right and left eyes will be considered as separate events. The following will be summarized and presented overall and by treatment group:

- The number and percentage of subjects experiencing an SAE.
- The number and percentage of subjects experiencing an SAE by preferred term and by severity of event.
- The number and percentage of subjects experiencing an SAE by preferred term and by relationship to study drug.

- The number and percentage of subjects experiencing an AE.
- The number and percentage of subjects experiencing an AE by preferred term and by severity of event.
- The number and percentage of subjects experiencing an AE by preferred term and by relationship to study drug.
- The number and percentage of AEs that cause a subject to discontinue study drug.
- The number and percentage of AEs leading to death.

13 Data Management

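### AE-caused discontinuation of study drug is reported as a percentage of AEs, not of patients, so the percentage can understate, reverse or overstate a difference between arms

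*SAP*

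**What the plan says.** SAP 11.1 and Protocol 12.6 carry the same list of eight safety summaries. The SAP introduces it with "The following will be summarized and presented overall and by treatment group".

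- Six lines (three for SAEs, three for AEs) count subjects, for example "The number and percentage of subjects experiencing an AE".
- The seventh counts events: "The number and percentage of AEs that cause a subject to discontinue study drug".
- The eighth does too: "The number and percentage of AEs leading to death".

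Three other provisions bear on the seventh line:

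- **Eyes.** Protocol 12.6 adds "Events in the right and left eyes will be considered as separate events". SAP 11.1 does not repeat this rule. Protocol 5 says "The assigned drop will be administered in both eyes throughout the study".
- **Dosing period.** Protocol 5 plans drops "for a total of 7 days of study drug administration".
- **AE period.** Protocol 5.4 says "All ocular adverse events will be recorded from randomization through Month 12".

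The nearest patient-level reports are elsewhere in the SAP. Section 9.1 gives subject frequencies for analysis populations, study withdrawals and major violations. The per-protocol population in section 7 requires full treatment but does not separate out patients who stopped because of an AE. Neither gives the proportion of patients who stopped the drops for that reason.

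**The concern.** Stopping the drops is something a patient does once, for both eyes. The natural question is what fraction of treated patients in each arm stopped because of an AE. The planned percentage answers a different one: of all AEs in an arm, what fraction led to a stop.

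That denominator is itself an outcome that treatment may change. If one arm has more AEs of every kind, its denominator grows with its numerator, and the percentage can stay level or fall while more of its patients stop. Two features of this trial add to the problem:

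- The denominator includes events long after dosing has ended. Several AEs listed in Protocol 6.1.2 are late by definition, such as pain or a poor refractive result from month 3 onwards. They cannot cause a stop, but they lower the percentage.
- Under the protocol's eye rule, one patient who stops for a bilateral event can put two AEs in the numerator.

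At stake is how clearly one descriptive tolerability summary reads, in a trial whose primary objective is safety.

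**Working it through.** The documents give no AE rate or discontinuation rate, so there is no planned figure to reproduce. All event counts below are assumed, to show how the percentage behaves.

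**Inputs**

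- Patients per arm: n = 60/2 = 30 (SAP 4.1 and 6, 1:1 allocation). Protocol 12.5 plans 63, which is 31 or 32 per arm.
- d = patients who stop because of an AE; s = AEs that cause a stop; E = all AEs in the arm.

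**Formulas**

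- Percentage as written: s/E.
- Per-patient percentage: d/n.
- With one stopping AE per patient (s = d), arm A shows an equal or lower percentage than arm B, although more of its patients stop, whenever E_A/E_B ≥ d_A/d_B.

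**Results, n = 30 per arm**

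| Case | Arm B: s/E | Arm A: s/E | Arm B: d/n | Arm A: d/n |
|---|---|---|---|---|
| Difference masked | 2/30 = 6.7% | 4/60 = 6.7% | 2/30 = 6.7% | 4/30 = 13.3% |
| Order reversed | 3/30 = 10.0% | 6/80 = 7.5% | 3/30 = 10.0% | 6/30 = 20.0% |
| Difference created | 2/28 = 7.1% | 4/30 = 13.3% | 2/30 = 6.7% | 2/30 = 6.7% |

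In the first row, every count in arm A is double that in arm B. Any common multiplier k cancels: 2k/30k = 6.7%. With 31 per arm the per-patient figures in that row become 2/31 = 6.5% and 4/31 = 12.9%.

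In the third row, two patients stop in each arm. Those in arm A stop for bilateral events (4 AEs), those in arm B for one-eye events (2 AEs). The eye rule alone produces the apparent difference.

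**Late events.** Take 2 against 4 stops and 30 AEs in each arm. As written this gives 2/30 = 6.7% against 4/30 = 13.3%.

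- Add 30 late AEs to both arms: 2/60 = 3.3% against 4/60 = 6.7%. Both percentages halve and their ratio is unchanged.
- Add 30 late AEs to arm A only: 2/30 = 6.7% against 4/60 = 6.7%. The difference disappears.

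Late events therefore dilute both percentages. They distort the ratio between arms only if their numbers differ by arm.

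**No distortion.** With equal AE totals and one stopping AE per patient, s/E and d/n order the arms the same way.

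**The case against.** The strongest reply is that nothing is hidden. The line prints the number as well as the percentage, by arm, in arms of nearly equal size. In the first two rows of the table a reader would see 2 against 4 and 3 against 6. Individual AE listings go to the DSMB, and the lines above it give the percentage of subjects with any AE or SAE. This stands. The percentage obscures the contrast, but the information is there. The adjacent number does not cure the eye problem, however, because it is a count of AEs: two patients with bilateral events would print as 4.

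It can also be said that the line carries little formal weight. Discontinuation is not among the safety endpoints in SAP 3.2.4. Protocol 5.4 ties tolerability to scheduled eye examinations. The study-stopping criterion in Protocol 11 counts patients, not AEs. This stands too. A reader might infer that the plan's main tolerability measure is compromised, but the documents give this line no such role.

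A reader might also infer that the error always favours pAF. It does not. Bilateral counting can make an arm look worse, and late events shift the comparison only if they differ by arm. The examples need unequal AE totals or unequal bilateral events, and the documents give no basis for predicting either.

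Finally, the denominator is not spelled out. Beside six lines worded for subjects, a percentage of AEs is the plain reading. If subjects were meant, the wording needs the same correction.

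**Conclusion.** The point holds as a reporting flaw. As worded, the percentage for AE-caused discontinuation is not a per-patient risk, and no other planned summary supplies one. It can mask a twofold difference (6.7% in both arms against 6.7% and 13.3% of patients), reverse one, or create one where none exists. These sizes rest on assumed counts with 30 patients per arm. The direction in the actual trial cannot be predicted.

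The consequence is limited. Counts by arm and DSMB listings remain available, and no endpoint, alpha, sample size or study-stopping rule uses this line. The documents do not support the stronger conclusion that a safety signal would go unseen. The death line has the same wording but matters little in practice, because Protocol 6.1 restricts recording to ocular AEs. The change is worth making because it is almost free.

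**What to change.** In SAP 11.1 and Protocol 12.6, replace the seventh line with: *number and percentage of Safety Population subjects in each arm with at least one AE leading to discontinuation of study drug, each subject counted once whether one or both eyes are affected*. List the number of such AEs beside it without a percentage. Reword the death line the same way for consistency.

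The cost is two lines of text in each document and a different denominator in one table. The existing line already requires each AE that caused a stop to be identified, so the new one needs only the link to the patient. The action-taken list in Protocol 6.1.3 has no separate category for stopping study drug, only a free-text other option, so the case report form should be checked to confirm that it captures this. The change affects reporting only and leaves clinical management as it is.

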3. STUDY OBJECTIVES AND ENDPOINTS

3.1 Study Objectives

3.1.1 *Primary Objective*

The primary objective of the pAF after PRK trial is to determine the safety of using processed Amniotic Fluid (pAF) in patients following PRK.

3.1.2 *Secondary Objectives*

The secondary objectives of the pAF after PRK trial are the following:

- To determine if pAF hastens re-epithelialization following PRK compared to placebo.
- To determine if pAF reduces post-operative pain following PRK compared to placebo.
- To determine if pAF affects visual outcome following PRK compared to placebo.
- To determine if pAF affects ocular surface staining and corneal regularity following PRK compared to placebo.

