8.4 Multiple Comparisons and Multiplicity

As there is a single primary efficacy endpoint for this study, adjustment for multiple comparisons will not be required for the primary analysis.

As a single efficacy outcome has been formally designated as the secondary efficacy outcome, adjustment for multiple comparisons will not be required for the secondary efficacy analysis.

No formal adjustment will be made for multiple comparisons in the reporting of treatment differences for exploratory outcomes. Reported analyses of exploratory outcomes will explicitly note that such outcomes are exploratory.

Safety outcomes for this study will be reported using unadjusted *p*-values for each individual comparison. However, all reports of these outcomes, to the DSMB and in published reports, will explicitly note that multiple safety outcomes have been evaluated.

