11.2 Ophthalmic Exam Findings

In addition to reporting of ocular AEs as above, numbers and proportions of participants in each study arm (if any) who had loss of best corrected vision in either eye by one line or more, compared to best corrected vision prior to treatment, at 6-month and 1-year evaluations will be reported. These numbers

will also be reported using eyes as numerator and denominator.

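### Safety is the primary objective, but no confidence interval is planned for any adverse-event rate or difference: the between-arm comparison is p-values beside counts and percentages

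*SAP*

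**What the plan says.** SAP 3.1.1 is explicit: "The primary objective of the pAF after PRK trial is to determine the safety of using processed Amniotic Fluid (pAF) in patients following PRK". The protocol (Synopsis and section 2) agrees.

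SAP 11.1 plans tables by arm, causality and severity, for example "The number and percentage of subjects experiencing an AE". It then adds a between-arm comparison: "Rates of adverse events will be compared between the two treatment groups using chi-squared type approaches". The preferred form is exact: "In most instances, exact approaches will be implemented that maximize the statistical power to detect a treatment difference", using Fisher's test with half the probability of the observed table subtracted (mid-p).

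SAP 8.4 sets the reporting format: "Safety outcomes for this study will be reported using unadjusted" p-values for each comparison, with a note that several safety outcomes were examined. SAP 11.2 reports numbers and proportions of participants "who had loss of best corrected vision in either eye by one line or more" at 6 months and 1 year, with no test and no interval.

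The only confidence interval named anywhere in the SAP is the Hodges-Lehmann interval for the exploratory pain outcomes (10.3.3). SAP section 6 and protocol 12.5 size the trial on re-epithelialization alone; the patients beyond the 56 completers are partly for extra safety data, but no precision or power target is attached to them.

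**The concern.** With about 30 patients per arm, a test of no difference is a weak tool for describing safety. When events are uncommon, a non-significant p-value is the likely result whether or not pAF is worse, and by itself it does not show how large an excess the data leave open. An interval does show that. As written, an exploratory outcome has a planned measure of uncertainty and the primary objective has none. The report could therefore give raw percentages and a column of mostly non-significant p-values without telling readers that an excess of, say, 25 to 30 percentage points remains compatible with the data.

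**Working it through.** **Inputs.**
- Patients per arm: 30, from 60 enrolled (SAP 6) at 1:1 (SAP 4.3). The protocol enrols 63 (12.5), hence 31 and 32. Completers: 28 per arm.
- Test: two-sided Fisher p minus half the probability of the observed table (SAP 11.1).
- Alpha for safety: not stated. Two-sided 0.05 is assumed, as the SAP uses for efficacy (10.1, 10.2).
- Control adverse-event rate: not stated in either document. Values from 1% to 20% are shown.

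**1. The plan's own figure.** There is none for safety. The efficacy table follows from: detectable difference = (1.960 + 0.842) × SD × √((1 + ICC)/2) × √(2/28). For SD 0.6 and ICC 0.5 this is 2.802 × 0.6 × 0.866 × 0.267 = 0.39 days, as printed. All 18 cells reproduce to within 0.01 day. The sizing is sound for re-epithelialization, but it does not address safety.

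**2. Planned test on 4/30 v 0/30.** Given 4 events in 60 patients, the probability that all fall on pAF is C(30,4)/C(60,4) = 27,405/487,635 = 0.0562. The opposite extreme is equally likely, so Fisher p = 0.1124. Mid-p = 0.1124 - 0.0562/2 = 0.084.

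**3. Interval for the same data.** Wilson limits are 5.3% to 29.7% for 4/30 and 0% to 11.4% for 0/30. Newcombe's method combines them:
- lower = 0.133 - √(0.080² + 0.114²) = -0.006
- upper = 0.133 + (0.297 - 0.133) = 0.297

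The excess is +13.3 points, with a 95% interval of -0.6 to +29.7.

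**4. Other splits at 30 per arm.**

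| pAF v placebo | mid-p | Difference (points) | Newcombe 95% interval |
|---|---|---|---|
| 5/30 v 0/30 | 0.039 | +16.7 | +2.0 to +33.6 |
| 6/30 v 1/30 | 0.080 | +16.7 | -0.3 to +34.2 |
| 6/30 v 2/30 | 0.204 | +13.3 | -4.7 to +31.3 |

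A 1/30 v 1/30 split leaves ±13.6 points.

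**5. No events on pAF.** The exact (Clopper-Pearson) two-sided 95% upper limit is 1 - 0.025^(1/30) = 11.6%. With 28 patients it is 12.3%.

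**6. Power of the mid-p test, 30 per arm.** This is the sum of both binomial distributions over all tables with mid-p ≤ 0.05.

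| Assumed control rate | Threefold excess | Fourfold excess |
|---|---|---|
| 1% | 0.1% | 0.5% |
| 2% | 1.8% | 5.0% |
| 5% | 16.2% | 33.5% |
| 10% | 42.5% | 74.3% |
| 15% | 68.6% | 95.4% |
| 20% | 87.2% | 99.8% |

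**7. Sensitivity to arm size and test.** At a 5% control rate, threefold/fourfold power is:
- 28 per arm: 14.4%/30.3%
- 32 pAF, 31 placebo: 18.8%/37.6%
- 31 pAF, 32 placebo: 26.7%/46.6%

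With unequal arms the two extreme tables are no longer equally likely. For 4/31 v 0/32 the observed table has probability C(31,4)/C(63,4) = 31,465/595,665 = 0.0528. The opposite extreme (0.0604) is more probable and is not counted, so mid-p = 0.0528/2 = 0.026. For 4/32 v 0/31 both extremes count and mid-p is 0.083. The choice of test matters too: an uncorrected chi-squared on 4/30 v 0/30 gives p = 0.038.

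**The case against.** A reader might infer that the plan judges safety by significance tests, or treats p > 0.05 as proof of safety. The documents do not say so. The formal hypotheses and the 0.05 rejection rule are written for efficacy only (SAP 10.1, 10.2). Safety has no hypothesis, no alpha and no success criterion. Protocol 5.4 says "Safety and tolerability will be evaluated by the PI from the findings of scheduled eye examinations", the DSMB reviews safety at about 5, 30 and 60 patients (SAP 5.1.1), protocol section 11 has a study-level discontinuation rule, and the count tables are reported regardless of any test. Reading non-significance as safety would be a misuse of the output that the plan neither prescribes nor rules out.

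A reader might also quote 16% to 34% as the trial's power to detect harm. That range rests on a 5% control rate that is in neither document. Over control rates of 1% to 20% the same test runs from under 1% to over 99%, and for a broad outcome such as any ocular event over 12 months the rate could exceed 5%. Nor is it a general rule that five pAF events against none are needed for significance: that holds at 30/30, but 4/31 v 0/32 is already significant.

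Finally, arm-level counts will be published, so a reader can compute intervals, and this is a small phase I/II trial. All of this stands and limits the size of the point. None of it supplies a planned measure of uncertainty for the primary objective, and small size is a reason to show what the data cannot exclude.

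**Conclusion.** The point holds as a gap in the safety analysis: no interval for any adverse-event rate, for any between-arm difference or for loss of best-corrected vision, and no stated precision target. This follows from the text and needs no assumption about event rates. The interval examples depend only on 30 patients per arm. The power figures depend in addition on an assumed two-sided 0.05 and an assumed control rate. They support one conclusion: for uncommon events (control rates of about 5% or less) the planned p-values would usually miss a threefold or fourfold excess, whereas for common events they would often detect it. All of these figures shift with the protocol's 63 patients. The case for intervals is the same across the whole range. This is a worthwhile improvement to analysis and reporting; trial conduct and data collection are unaffected.

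**What to change.** In SAP 11.1 and 11.2, for any ocular adverse event, any serious adverse event, each event listed in protocol 6.1.2 and loss of best-corrected vision, report:
- the patient-level risk difference (pAF minus placebo) with a 95% score-type interval, with Newcombe or Miettinen-Nurminen chosen in advance;
- the pAF event rate with an exact 95% interval.

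Keep the mid-p values as a flag. In SAP 8.4, state that a non-significant comparison will not be read as evidence of safety.

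The cost is some SAP wording and two more table columns. The intervals will look wide, which is an accurate picture of what a trial of this size can show.
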